ATTACHMENT 11: SCADDING CXR SCORE

Stage 0 radiographic sarcoidosis. This normal chest x-ray may be observed in 5 to 15% of cases.

Stage I radiographic sarcoidosis. Bilateral hilar lymphadenopathy with clear lung fields.

Source: Semin Respir Crit Care Med © 2007 Thieme Medical Publishers

Stage II radiographic sarcoidosis. Combined hilar lymphadenopathy and upper lung zone predominant interstitial infiltrates.

Source: Semin Respir Crit Care Med © 2007 Thieme Medical Publishers

Stage III/IV radiographic sarcoidosis. Note the upper lung zone volume loss, upward retraction of the hilae, and tenting of the hemidiaphragms.

Source: [Scadding, 1961](#)

ATTACHMENT 12: SIX-MINUTE WALK TEST

Visit 1, 8, 11

Borg Scale

0	Nothing at all
0.5	Very, Very Slight (just noticeable)
1	Very Slight
2	Slight
3	Moderate
4	Somewhat Severe
5	Severe (heavy)
6	
7	Very Severe
8	
9	
10	Very, Very Severe
	Maximal

At the beginning of the 6-minute walk test, show the scale to the patient and ask the patient this: "Please grade your level of shortness of breath using this scale". Then ask this: "Please grade your level of fatigue using this scale."

After the posttest recovery period, remind the patient of the breathing number that they chose before the exercise and ask the patient to grade their breathing level again. Then ask the patient to grade their level of fatigue, after reminding them their grade before the walk test.

Vital Signs	Baseline	Six minutes	1 Minute after walk
Heart Rate			
Oxygen Sat			
Lpm SA O ₂			
Borg Score (Shortness of Breath)			
Borg Score (Level of Fatigue)			

Laps		# of Rests	
------	--	------------	--

Limiting factors to test:

SOB LOW SpO₂ Heart Disease Desaturation <80%
 Other: _____

Total distance walked _____ Feet _____ Meters

Signature Page for VV-CLIN-023158 v2.0

Approval	[REDACTED]
	Clinical 18-May-2020 16:35:27 GMT+0000

Signature Page for VV-CLIN-023158 v2.0

11.2. GENETIC PROFILE	31
12. INTERIM ANALYSIS.....	31
13. CHANGES IN THE PLANNED ANALYSIS.....	31
14. REFERENCES	31
15. APPENDICES	33
15.1. DATE IMPUTATION GUIDELINE	33
15.1.1. Adverse Events	33
15.1.2. Prior/Concomitant Medications.....	33
15.2. CALCULATION OF PATIENT-REPORTED OUTCOMES AND SYMPTOM QUESTIONNAIRES	35
15.2.1. Steroid Toxicity Questionnaire.....	35
15.2.2. King's Sarcoidosis Questionnaire	35
15.2.3. Fatigue Assessment Scale (FAS).....	50
15.2.4. Patient Global Assessment Score	50
15.2.5. Physician Global Assessment Score.....	50
15.2.6 Medical Research Council Dyspnea Scale	50
15.2.7 Leicester Cough Questionnaire	50
15.3. SCHEDULE OF STUDY EVENTS	52
15.4. SAS PROCEDURES	55

List of Abbreviations

6MWT	Six-Minute Walk Test
AE	adverse event
ANOVA	analysis of variance
AR1	first-order autoregressive
ATC	Anatomical Therapeutic Chemical
BMI	body mass index
CXR	chest x-ray
CS	Compound Symmetry
DLCO	Diffusing capacity of the lungs for carbon monoxide
ECG	electrocardiogram
eCRF	electronic case report form
ePOST	extrapulmonary Physician Organ Severity Tool
FAS	Fatigue Assessment Scale
FEF	forced expiratory flow
FEV1	forced expiratory volume in 1 second
FVC	forced vital capacity
Hb	hemoglobin
HbA1c	hemoglobin (glycosylated)
HRCT	high-resolution computed tomography
IMP	investigational medicinal product
KSQ	King's Sarcoidosis Questionnaire
LCQ	Leicester Cough Questionnaire
LLoQ	lower limit of quantitation
LOCF	last observation carried forward
LS	least square
MMRM	mixed model with repeated measures
MedDRA	Medical Dictionary for Regulatory Activities
mITT	modified intent-to-treat
PEFR	peak expiratory flow rate
PFT	pulmonary function test

PT	preferred term
RV	residual volume
SAE	serious adverse event
SAP	Statistical Analysis Plan
SC	subcutaneous
SD	standard deviation
SE	standard error
SI	International System of Units
SOC	system organ class
STS	sarcoidosis treatment score
TEAE	treatment-emergent adverse events
TLC	total lung capacity
TTR	time to response
ULoQ	upper limit of quantitation
UN	unstructured
VA	alveolar volume
WHO	World Health Organization
WPAI	Work Productivity and Activity Impairment

1. Introduction

The purpose of the Statistical Analysis Plan (SAP) is to describe the analyses and data presentations for the Sponsor's protocol MNK14344100. This SAP outlines the types of analyses that will address the study objectives and explains in detail how the data will be handled and analyzed. It contains the definitions of analysis populations and statistical methods for the analysis of safety and efficacy.

2. Study Objectives

The objective of the study is to evaluate the efficacy and safety of Acthar® Gel (Acthar) in the treatment of pulmonary sarcoidosis.

3. Investigational Plan

3.1. Overall Study Design and Plan

This is a Phase 4, multicenter, randomized, double-blind, placebo-controlled exploratory study evaluating the efficacy and safety of Acthar in the treatment of pulmonary sarcoidosis. The study will have 3 phases: screening (up to 28 days); double-blind treatment (Visit 2 to Visit 8, 24 weeks); and an optional open-label extension (Visit 9 to Visit 11, 24 weeks). A follow-up visit will be conducted at 4 weeks (\pm 2 days) after the last dose of investigational medicinal product (IMP) is administered.

[figure not shown]
An overview of the study is presented in [Figure 1](#).

Subjects who meet all eligibility criteria will be randomly assigned to receive either 1 mL (80 U) of Acthar or 1 mL of a matching placebo subcutaneously (SC) twice weekly. Following the completion of the double-blind phase, subjects will be invited to continue participation in an optional Open-label Extension Phase (Visit 9 to Visit 11, 24 weeks). Subjects who decline participation in the open-label extension phase, or those ineligible, will have their End-of-Treatment visit during Visit 8.

Dose reduction of 50% may be implemented once during the study if a subject meets one of the prespecified safety criteria (refer to protocol Section 9.1). Once dose reduction is implemented, subjects will remain on the 40 U or matching placebo twice weekly for the remainder of the study.

The schedule of study events is presented in [Appendix 15.3](#).

Figure 1: Study Overview

Note: Visit 8 is the primary efficacy evaluation time point. Additional analyses of long term efficacy and safety of subjects participating in the Open-label Extension Phase will be conducted at the completion of Visit 12. PFT and sample collection for assessment of biomarkers will be performed every 12 weeks. HRCT will be performed at Screening (Visit 1) and every 24 weeks thereafter (Visits 8 and 11).

3.2. Study Endpoints

3.2.1. Efficacy Endpoints

The endpoints for the efficacy objective are:

- Sarcoidosis treatment score (STS) response rate at 24 weeks (Visit 8).
- STS response rate at 48 weeks (Visit 11).
- Physician and subject independent responses to the question “Would you choose to continue current treatment?” at 24 and 48 weeks.
- Time to response (TTR) as evaluated at earlier time points (Weeks 4 to 20) as determined by the investigator based on clinical judgment and the following parameters:
 - Patient reported outcomes.
 - Corticosteroid tapering.
 - Patient Global Assessment.
 - Physician Global Assessment

- Pulmonary function test (PFT) at applicable time points.
- Extrapulmonary response by extrapulmonary Physician Organ Severity Tool (ePOST).
- Supportive efficacy endpoints per applicable time points.
 - Six-minute walk test (6MWT).
 - Symptom relief (Leicester Cough Questionnaire, Medical Research Council Dyspnea Scale, steroid toxicity questionnaire).
 - Chest x-ray (CXR) (including Scadding score).
- Percentage change in overall diffusion capacity of the lung for carbon monoxide (DLCO).
- Percentage of subjects with improvement in DLCO of $\geq 5\%$; $\geq 10\%$; and $\geq 15\%$.
- Percentage change in overall forced vital capacity (FVC).
- Percentage of subjects with improvement in FVC of $\geq 5\%$, $\geq 10\%$, and $\geq 15\%$.
- Percentage of subjects with improved/stable/deteriorate side-by-side comparison of high-resolution computed tomography (HRCT) on a 5-point Likert score: much worse; worse; unchanged; better; much better (central reader).
- Percentage of subjects with improved/stable/deteriorated side-by-side comparison of CXRs on a 5-point Likert score: much worse; worse; unchanged; better; much better (central reader).
- Percentage change in Scadding score (side-by-side comparison of CXRs by a central reader).
- Percentage change in patient-reported outcomes and symptom questionnaires.
- Percentage failed corticosteroid taper.
- Time to failed corticosteroid taper (for subjects failing taper).
- Change from baseline in Work Productivity and Activity Impairment (WPAI) over time

3.2.2. Biomarker and Genetic Endpoints

Biomarkers levels will be compared between baseline, and every 12 weeks (up to 48 weeks for those subjects participating in the optional open-label extension phase). Serum aliquots will be kept for each of these time points. Possible biomarkers include angiotensinogen, sIL-2R and vitamin D 1, 25. The final selection of biomarkers will be made based on the scientific knowledge and emerging guidance closer to the completion of the study.

Genomic profile (optional) will be assessed based on the understanding of genetic factors at the time of study completion.

3.2.3. Safety Endpoints

Overall safety will be determined by the incidence, severity and relationship of AEs, physical examinations, vital signs, clinical laboratory abnormalities, and imaging.

4. General Statistical Considerations

4.1. Sample Size

Formal sample size calculations were not performed. The sample size is based on recent literature of comparative studies ([Gibson et al., 1996](#); [Baughman et al., 2006](#); [Judson, 2014](#)) in sarcoidosis. There are 55 subjects randomized to this study.

4.2. Randomization, Stratification, and Blinding

An interactive telephone/web response system will be used to allocate eligible subjects to each treatment group. Subjects will be randomized according to computer-generated allocation scheme to receive either Acthar Gel 1 mL (80 U) or placebo 1 mL administered twice a week in a 1:1 ratio. Both investigators and the subjects will be blinded to the treatment assignment. A block randomization will be performed.

4.3. Reporting Conventions

The following reporting conventions apply generally to tables, listings, and figures:

- All by-visit summaries and analyses will be provided separately for the double-blind treatment phase and the open-label extension phase, unless otherwise specified. Only subjects who continued to the open-label extension phase will be included in the summaries of open-label extension phase based on the open-label safety populations.

- For subjects who continued into the open-label extension phase, the first dose of IMP at the open-label extension phase will be used as the cutoff date. Since the first dose administration date at the open-label extension phase is not collected electronically, and the dosing schedule is twice/week, either the first IMP kits and equipment dispense date or the next date after completion date of double-blind phase, whichever is the later date, has been used as the best estimate of the first dose of IMP in the open label extension phase. The assessments collected before the cutoff date will be summarized in the double-blind treatment phase and the assessments collected on or after the cutoff date will be summarized in the open-label extension phase, unless specified otherwise. Subjects who did not continue into the open-label extension phase will be summarized in the double-blind treatment phase only.
- Summaries for the double-blind treatment phase will be based on the treatments that the subjects actually received at the double-blind treatment phase. Summaries for the open-label extension phase will also be based on the treatment sequences that the subjects actually received during overall study phase, e.g. Acthar/Acthar and Placebo/Acthar.
- Study Day 1 is defined as the date of the first dose of IMP at the double-blind treatment phase. Study days are calculated as the difference between the date of interest and Study Day 1 plus 1 day. For events before Study Day 1, study days will be calculated as the difference in days between Study Day 1 and the date of interest. The day before the date of the first dose at the double-blind treatment phase will be defined as Day -1. This means there will be no study Day 0.
- Two baselines, baseline of overall study and baseline of active treatment, have been defined. Baseline of overall study is defined as the last assessment prior to the first dose of IMP at the double-blind treatment phase. Baseline of active treatment is defined as the last assessment prior to the first dose of active treatment in either the double-blind treatment phase or the open-label extension phase. All the analysis in the open-label extension phase that involves presenting change and/or percent change from baseline will present change/percent change from both baselines.
- Summary statistics will be provided for all study variables with descriptive statistics (number of subjects, mean, standard deviation (SD), median, minimum,

and maximum) for numerical (or continuous) variables. Frequency and percentages will be calculated for categorical variables.

- Unless specified otherwise for a given analysis, all statistical tests, when applicable, will be 2-sided with a significance level of 0.05.
- All data collected will be presented in listings, sorted by treatment group, subject identifier and date/time of procedure or event, if applicable.

All analyses will be conducted using SAS® Version 9.4 or higher. The Medical Dictionary for Regulatory Activities (MedDRA) version 23.0 will be used for coding adverse events (AEs), and medical and surgical histories. Prior or concomitant medication data will be coded according to the Anatomical Therapeutic Chemical (ATC) coding scheme of the World Health Organization (WHO) Drug Dictionary (Enhanced B2 dated March 2018 version, or higher) level 2 term.

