10.1. Adverse Events

An AE is any untoward or undesirable medical occurrence in a subject who is administered an IMP, which does not necessarily have to have a causal relationship with this treatment.

A TEAE is defined as an event that begins or worsens on or after the start of study drug through 30 days after the date of the last dose. The first dose of IMP at the open-label extension phase will be used as cutoff date, the TEAEs started before the cutoff date will be summarized in the double-blind treatment phase and the TEAEs started on or after the cutoff date will be summarized in the open-label extension phase; Subjects who did not continue into the open-label extension phase will be summarized in the double-blind treatment phase only.

If a subject experiences the same AE more than once with different severity, then the event with the highest severity level will be tabulated in “by severity” tables. If a subject experiences the same AE more than once with different relationship to study drug, then the event with the most related level will be tabulated in “by relationship” tables. Note that AEs with a missing severity will be considered as severe, and AEs with missing relationship will be considered as related to study drug. Adverse events are considered treatment-related if the relationship to study drug is possibly related, related or missing.

The incidence of AEs will be summarized in tables with the number and percentage of subjects with AEs by SOC and PT. At each level of SOC or PT, a subject with multiple events will only be counted once per SOC or PT. Percentages of subjects with AEs will be calculated out of the number of subjects in the safety population. SOC will be presented alphabetically and PTs within each SOC will be presented in decreasing order of frequency based on the total number of subjects with each AE in the Acthar group. The following categories of TEAE will be summarized by SOC and PT by treatment group and total for the double-blind treatment phase and the open-label extension phase separately:

- TEAEs
- TEAEs by severity (Mild, Moderate, and Severe)
- TEAEs by relationship (Not Related, Unlikely Related, Possibly Related, and Related)
- Treatment related TEAEs
- Serious TEAEs
- Serious TEAEs by relationship (Not Related, Unlikely Related, Possibly Related, and Related)
- TEAEs leading to study drug discontinuation
- TEAEs leading to death

Overview tables of the above categories will also be provided.

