All AEs will be presented in a data listing by study phase and TEAEs will be flagged in the listing.

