ⁿ Full pulmonary function test (PFT) results will include forced expiratory volume in 1 second (FEV1), forced vital capacity (FVC), FVC % predicted (NHANES III reference values), FEV1/FVC ratio, peak expiratory flow rate (PEFR) or forced expiratory flow at maximum effort (FEF_{max}), total lung capacity, residual volume, diffusing capacity of the lungs for carbon monoxide (DLCO; uncorrected for Hb), DLCO: % predicted and DLCO/alveolar volume.

^o High-resolution computed tomography (HRCT) should be performed within 28 days of Day -1. Both CXR and HRCT should be evaluated side by side by investigator/radiologist/central reader for determining if the condition is improving, stable, or deteriorating based on a 5-point Likert score: much worse; worse; unchanged; better; much better. The CXR will also include Scadding scoring ([Attachment 11](#)).

^p The Six Minute Walk Test (6MWT) would be performed according to the ATS protocol ([Attachment 12](#)). Reasons for not performing the 6MWT will be captured in eCRF.

^q Subjects (and/or caregivers) will be trained on SC injections using the training tools provided separately. Additional training may be provided during Visit 2 before randomization occurs. SC injections training may be forgone if either the subject or caregiver is a medically trained professional.

^r The importance of adhering to treatment will be encouraged at every visit. At Visit 8, IMP will only be dispensed for subjects participating in the optional Open-label Extension Phase.

^s Dosing will begin after Visit 2 procedures are completed and subject is randomized. The first dose of study drug for all subjects will be administered in the clinic and the subject will be observed for at least 1 hour after dosing. For subjects entering the Open Label Extension, the first dose given at Week 24 will be administered in the clinic and the subject will be observed for at least 1 hour after dosing. All other doses will be administered by the subject or the subject's caregiver at home 2×/week but not on visit days (see [Section 13.3](#)).

^t Corticosteroid taper will follow the specified algorithm. Corticosteroid tapering at Visit 8 is done for patients entering open label extension only. Reasons for determining worsening will be captured in the eCRF (FVC, DLCO, imaging, symptoms, other). Justification for any deviations will also be captured in the eCRF.

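### If double-blind completion is recorded at Visit 8, the SAP's estimated open-label start falls a day after the supervised Acthar dose, so a former placebo subject's same-day reaction is counted as a double-blind placebo event (probably few subjects, cheap to correct)

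*SAP*

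**What the plan says.** SAP 4.3 makes the first open-label dose the boundary between the two phases. It then says that "the first dose administration date at the open-label extension phase is not collected electronically" and substitutes the later of two dates: first dispensing of open-label kits, or "the next date after completion date of double-blind phase, whichever is the later date, has been used as the best estimate". For data in general, "The assessments collected before the cutoff date will be summarized in the double-blind treatment phase". SAP 10.1 applies the same boundary to adverse events: "the TEAEs started before the cutoff date will be summarized in the double-blind treatment phase". Under SAP 4.3 and 4.4.2, double-blind summaries label each subject by the treatment received in that phase.

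SAP 3.1 describes the phase as "double-blind treatment (Visit 2 to Visit 8, 24 weeks"), but no section defines the recorded completion date.

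Footnote s of the SAP's own schedule (15.3) states: "For subjects entering the Open Label Extension, the first dose given at Week 24 will be administered in the clinic". Protocol 11.5 lists this dose among the Visit 8 procedures, with at least one hour of observation. Protocol 12.3 gives the purpose as watching for allergic or anaphylactic reactions. The general rule against dosing on visit days does not apply here, because protocol 12.3 and footnote s confine it to all other doses.

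**The concern.** The estimated start date and the scheduled dose do not fit together. A rule that can return no date earlier than the day after completion cannot return the day of a dose given at the completion visit. The misfiled window includes the observation hour that the protocol amendment introduced. Protocol Appendix 1 explains that former placebo subjects should be monitored at their first Acthar exposure as closely as subjects who started on Acthar.

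What is at stake is the attribution of acute reactions. For a former placebo subject the error runs one way: an event after Acthar is shown under placebo in the double-blind table and is missing from the Placebo/Acthar column of the open-label table. The same cutoff feeds the related, serious and discontinuation TEAE tables in SAP 10.1. For an Acthar/Acthar subject only the phase changes.

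**Working it through.** There is no planned figure to reproduce. The check is date logic plus one scale calculation.

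**Inputs**
- Cutoff = max(dispense date, completion date + 1 day): SAP 4.3.
- Extension kits are dispensed at Visit 8: protocol 11.5 and schedule footnote r.
- First open-label dose is given at Visit 8: protocol 11.5 and SAP 15.3, footnote s.
- An adverse event with onset before the cutoff is double-blind; on or after it, open-label: SAP 10.1.
- Completion date: not defined, so varied below.

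**Classification of an adverse event starting on Visit 8 (V8), with kits dispensed on V8**

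| Completion recorded | Cutoff | Same-day event counted as |
|---|---|---|
| V8 − 3 | max(V8, V8 − 2) = V8 | open-label |
| V8 − 1 | max(V8, V8) = V8 | open-label |
| V8 | max(V8, V8 + 1) = V8 + 1 | double-blind |
| V8 + 1 | max(V8, V8 + 2) = V8 + 2 | double-blind |

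If completion is recorded at Visit 8 or later, no dispense date can bring the cutoff back to Visit 8. If completion is recorded after Visit 8, the misfiled window also extends past the day of the dose. If completion is recorded before Visit 8 and kits are dispensed at Visit 8, the error does not arise.

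The misfiled event still counts as a TEAE, because it begins after the start of study drug. It therefore enters the double-blind table under the subject's double-blind treatment.

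**Scale.** SAP 4.1 says: "There are 55 subjects randomized to this study". At 1:1, 55/2 = 27.5, so arms of 27 and 28 are assumed; the documents do not give the actual split. One event is 1/28 = 3.6% to 1/27 = 3.7% of the placebo arm. This is a ceiling for any one row, because SAP 10.1 counts a subject once per SOC and once per PT. A row moves only if that subject had no earlier double-blind event in it.

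**Number exposed.** The supervised Visit 8 dose came in with Version 2 Amendment 1 (protocol Appendix 1), so only subjects entering the extension after that are exposed. The same amendment added the WPAI at Visits 1 to 11. SAP 13 drops the WPAI analysis because very few subjects completed it. A subject who reached Visit 8 under the amended protocol should have been offered the WPAI there, so few supervised Visit 8 doses are likely. This is indirect, since the WPAI may be missing for other reasons, but it is the best indicator the documents contain.

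**The case against.** The next-day rule has a good purpose. Visit 8 assessments are the double-blind endpoint data. Under SAP 4.3, assessments on or after the cutoff go to the open-label phase, so a cutoff of Visit 8 would misplace them. The rule also suits subjects who entered the extension before the amendment and had no supervised Visit 8 dose; they may be most of the extension. SAP 4.3 is open about the missing date. All of this stands, and it is why the rule should be kept for those uses. None of it justifies applying the same date to adverse events that start after a supervised dose.

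It can also be said that nothing is lost. That is right: "All AEs will be presented in a data listing by study phase and TEAEs will be flagged in the listing", listings are sorted by date and time where applicable (SAP 4.3), and protocol 16.4 requires serious events to be reported within 24 hours. But the listing is itself split by phase, so the reader must notice the date to see the misplacement.

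A further point is that SAP 10.1 names the first dose itself as the cutoff. SAP 4.3 says that date is not available electronically, so in practice the estimate is used.

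Finally, the documents do not say that sites recorded the time of the supervised dose. Protocol 12.6 has the diary record each administration but does not mention time. That stands, and the fix needs a default for it.

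**Conclusion.** The point holds as a cheap improvement. On the natural reading that completion is recorded at Visit 8, SAP 4.3 and 10.1 place a former placebo subject's same-day reaction to supervised Acthar in the double-blind placebo column. Each such event changes a given row by at most 3.6 to 3.7 points, under assumed arms of 27 to 28 and with no earlier event in that row. The conclusion rests on the undefined completion date and on the dose being given at Visit 8 as scheduled.

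A reader might infer more, and the documents do not support it:
- **That misplacement is likely or can be given a probability.** Neither the number of former placebo subjects dosed in clinic at Visit 8 nor a same-day event rate is given, and the WPAI remark points to few subjects.
- **That every extension entrant is affected.** Pre-amendment entrants had no required supervised Visit 8 dose.
- **That the safety comparison is materially biased or that efficacy is touched.** The safety tables are descriptive, and Visit 8 assessments stay in the double-blind phase under this rule.

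**What to change.** 1. **SAP 4.3.** Define the double-blind completion date. Keep the next-day cutoff for assessments, stating that Visit 8 assessments belong to the double-blind phase. Keep it also for subjects with no supervised Visit 8 dose.
2. **SAP 10.1.** For subjects dosed in clinic at Visit 8, assign an adverse event with onset on that date to the open-label phase if its recorded onset time is at or after the dose. Protocol 16.4 already requires onset date and time.
3. **Default.** Where the order cannot be established, assign the event to the open-label phase and flag it in the adverse event listing. Duplicate phase tables are not needed.

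The cost is text in two SAP sections, and a dose date (with time, if noted) retrieved from the diary or site source for what are probably a few subjects. No procedures are added. The downside of the default is that an event that truly began before the dose on Visit 8 would be counted as open-label; the flag lets a reader see this.
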